8. ADVERSE EVENTS AND SERIOUS ADVERSE EVENTS

Overview of Adverse Event Reporting

Timely and complete reporting of safety information assists study management in identifying any untoward medical occurrence. This contributes to patient safety, regulatory compliance and improvements in study design or procedures. In addition, close attention to AEs provides valuable information about the safety and tolerability of study drugs. This study specific safety plan is designed to collect information on the safety and tolerability of the study medications; thus, reporting will be conducted in accordance with the requirements of GCP and other regulatory requirements governing clinical research in the US.

Definitions and recording requirements for this trial are based on the International Conference on Harmonisation Efficacy Guideline 2a: Pharmacovigilance: Clinical Safety Data Management: Definitions and Standards for Expedited Reporting (ICH-E2A), the Code of Federal Regulations (21 CFR 312.32) and CSP Global Standard Operation Procedure (SOP) 3.6.

In HITCH, patients will receive a regimen of FDA approved commercially available degarelix for injection (Firmagon[®]) 240 mg for subcutaneous use or matching placebo. Local Study Investigators, with assistance from their local SC, are responsible for collecting AE and SAE information regarding the patients at their sites.

Non-serious AEs and SAEs will be collected from the time of randomization until 60 days after the last dose of study medication. Throughout the specified duration of AE and SAE collection, data will be collected through spontaneous local SC/LSI/Co-I contact, during in-person study visits, and gathered during telephone contacts and medical record reviews when performed (**see Table of Scheduled Events**). AEs will be collected based on a review of the electronic medical record. If a patient receives care at a non-VA facility for an AE or SAE, study staff should obtain the requisite release of information form(s) from the patient and acquire the pertinent medical records from the facility.

Adverse events that are open will require follow-up reports (if necessary) every 30 days until resolved or until the end of the trial.

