Adverse events reported to study staff and deemed related to the study drug(s) and all SAEs will be recorded on an AE or SAE form (respectively) and documented in source records (e.g., the electronic VA medical record and/or the patient's study record). In this way, the site creates a permanent record that provides information on the patient's clinical course while in the study.

Adverse Events (AEs)

An AE is any untoward physical or psychological occurrence in a human participating in research or associated with the use of a drug in a human. An AE can be any unfavorable and unintended event, including an abnormal laboratory finding, symptom, or disease associated with the research or the use of a medical investigational test article. An AE does not necessarily have to have a causal relationship with the research or medical investigational test article. (See 21 CFR 312.32(a) and VHA Handbooks 1058.01 and 1200.05)

Severity of an Adverse Event

Adverse events will be graded according to CTCAE v5.0.

All adverse events that are related to the study intervention or procedures are recorded at each research assessment visit (description, severity, relationship to study intervention, date onset, date resolution).

The following categories are used to convey the severity of an adverse event:

- Grade 1 Mild; – Events require minimal or no treatment and do not interfere with the patient's daily activities.
- Grade 2 Moderate; – Events result in a low level of inconvenience or concern with the therapeutic measures. Interferes with normal daily activities to some extent.
- Grade 3 Severe; – Events interrupt a patient's usual daily activity and may require systemic drug therapy or other treatment. May severely interfere with or prevent normal daily activities
- Grade 4 Life-threatening consequences; – Events requiring urgent intervention
- Grade 5 Death related to AE.

Serious Adverse Event (SAEs)

An AE is considered an SAE if, in the view of either the investigator or sponsor, it results in any of the following outcomes:

- Death;
- A life-threatening AE;

NOTE: The term “life-threatening” in the definition of “serious” refers to an event in which the patient was at risk of death at the time of the event; it does not refer to an event which hypothetically might have caused death if it were more severe.

- Inpatient hospitalization or prolongation of existing hospitalization;

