#### **2.4.4 Safety Outcome Variables**

Safety measures include study-related adverse events (AE) and serious adverse events (SAE), and AE with special interest in the drug toxicity.

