#### **2.5.3. Safety Assessment**

Timely and complete reporting of safety information assists study management in identifying any untoward medical occurrence. This contributes to patient safety,

regulatory compliance and improvements in study design or procedures. In addition, close attention to AEs provides valuable information about the safety and tolerability of study drugs. This study specific safety plan is designed to collect information on the safety and tolerability of the study medications; thus, reporting will be conducted in accordance with the requirements of GCP and other regulatory requirements governing clinical research in the US. In HITCH, patients will receive a regimen of FDA approved commercially available degarelix for injection (Firmagon®) 240 mg for subcutaneous use or matching placebo. Local Study Investigators, with assistance from their local SC, are responsible for collecting AE and SAE information regarding the patients at their sites. Non-serious AEs and SAEs will be collected from the time of randomization until 30 days after the last dose of study medication. Throughout the specified duration of AE and SAE collection, data will be collected through spontaneous local SC/LSI/Co-I contact, during in-person study visits, and gathered during telephone contacts and medical record reviews when performed (see Table of Scheduled Events). AEs will be collected based on a review of the electronic medical record. Adverse events that are open will require follow-up reports (if necessary) every 30 days until resolved or until the end of the trial. Adverse events reported to study staff and deemed related to the study drug(s) and all SAEs will be recorded on an AE or SAE form (respectively) and documented in source records (e.g., the electronic VA medical record and/or the patient's study record).

Severity of an Adverse Event The following categories are used to convey the severity of an adverse event:

- Grade 1 Mild; – Events require minimal or no treatment and do not interfere with the patient's daily activities
- Grade 2 Moderate; – Events result in a low level of inconvenience or concern with the therapeutic measures. Interferes with normal daily activities to some extent
- Grade 3 Severe; – Events interrupt a patient's usual daily activity and may require systemic drug therapy or other treatment. May severely interfere with or prevent normal daily activities

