Unanticipated Adverse Event An AE that is new or greater than previously known, in terms of nature, severity, or frequency of occurrence, or any other unanticipated serious problem associated with the investigation that relates to the rights, safety, or welfare of participants, as documented in the protocol or other materials approved by the IRB of record or the characteristics of the study population.

Adverse Events of Special Interest Cardiac arrhythmias and thromboembolic events will be considered AEs of special interest. Any cardiac arrhythmia or thromboembolic event of grade 3-5 according to Common Terminology Criteria for Adverse Events version 5.0 (CTCAE v5.0; see Appendix 5.4) will be reported in a manner similar to SAEs, whereby the event will be reported to the HITCH reporting system within 3 calendar days of the Study Site Personnel becoming aware of the event.

All adverse events that are related to the study intervention or procedures are recorded at each research assessment visit (description, severity, relationship to study intervention, date onset, date resolution).

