#### 3.8.1 AE and SAE analyses

Adverse events (AE) and serious adverse events (SAEs) are defined by the ICH for Clinical Safety Data Management (ICH-E2A), the Food and Drug administration as described in the section 9. Incidence of AE/SAEs will be summarized for each treatment group by body system and MedDRA term. The number and percentage of participants with each body system and MedDRA term will be presented for each group. Pearson  $\chi^2$  test and/or Fisher Exact test were used to compare the frequency difference of AE and SAE between the treatment groups in System of Body (SOC) and Preferred Terms (PT) levels. Tables to summarize the incidence rates will be created for each of the following groups: Total AE and SAE, AE and SAE by relationship to study treatment, AE and SAE leading to premature discontinuation, AE and SAE presented in descending order of frequency by MedDRA term (no body systems shown). AE and SAE that led to premature discontinuation from the study will be listed. These listings will contain details about the SAEs such as outcome and relationship to study treatments. Other supportive data, such as the participant's age, will be given. All AE and SAE will be coded with MedDRA (updated version) and listed by participant. Tables to summarize the incidence rates will be created for each of the following groups:

- AE and SAE (Table 3.8.1a-b)
- AE and SAE by relationship to study treatment (Tables 3.8.2a-b)

- AE and SAE leading to premature discontinuation (Table 3.8.3a-b)
- AE and SAE presented in descending order of frequency by MedDRA term (no body systems shown) (Table 3.8.4a-b)

AE and SAE that led to premature discontinuation from the study will be listed.

These listings will contain details about the AE/SAEs such as outcome and relationship to study treatment. Other supportive data, such as the participant's age, will be given. All AE/SAEs will be coded with MedDRA (updated version) and listed by subject (Table 3.8.5).

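### The AE form takes a non-serious event only if a site judges it drug-related, which conflicts with the unfiltered collection rule and with the planned total-AE and by-relationship comparisons

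*Protocol*

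**What the plan says.** Two sets of statements stand side by side.

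**Limited to related events.** Protocol section 8 (Overview of Adverse Event Reporting) gives the form rule: adverse events "deemed related to the study drug(s) and all SAEs will be recorded on an AE or SAE form". SAP 2.5.3 carries the same sentence. Both documents add a visit-level rule: "All adverse events that are related to the study intervention or procedures are recorded at each research assessment visit". SAP 2.4.4 defines the outcome in the same way: "Safety measures include study-related adverse events (AE) and serious adverse events (SAE"), plus AEs of special interest. SAP 3.8 uses similar wording. Under Protocol section 8, the DMC receives related AEs and all SAEs.

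**Not limited.** The protocol's Overview also says: "Non-serious AEs and SAEs will be collected from the time of randomization until 60 days after the last dose of study medication". SAP 2.5.3 has the same sentence with a different window: "Non-serious AEs and SAEs will be collected from the time of randomization until 30 days after the last dose of study medication". The protocol's definition of an AE states: "An AE does not necessarily have to have a causal relationship with the research or medical investigational test article". SAP 3.8.1 plans incidence tables for "Total AE and SAE, AE and SAE by relationship to study treatment", with chi-square or Fisher tests between arms. Protocol section 10 (AE and SAE analyses) plans the same tables.

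**The concern.** In acutely ill inpatients the background rate of adverse events is high, and a single case seldom shows whether drug or disease was the cause. The randomised comparison of all events between arms answers that question without individual attribution. If attribution decides whether an event is entered at all, the comparison is made on a set already filtered by site judgement.

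The planned table labels do not tell the reader this. A table headed as total AEs that holds only related non-serious events invites the conclusion that other non-serious events did not differ between arms, when they were never entered. The DMC summaries carry the same restriction.

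**Working it through.** The plan states no figure to reproduce. The check is to follow each class of event from occurrence to the safety tables under the form rule as written.

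| Class of event | Reaches a form or report? | Source |
|---|---|---|
| SAE, any attribution | Yes | Protocol 8; SAP 2.5.3 |
| Grade 3-5 arrhythmia or thromboembolic event, any attribution | Yes, within 3 calendar days | Protocol 8; SAP 2.5.3 |
| Other non-serious AE, judged definitely or possibly related | Yes | Protocol 8; SAP 2.5.3 |
| Other non-serious AE, judged not related | No | Protocol 8; SAP 2.5.3 |

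**Step 1: total AEs.** The SAE part is complete. The non-serious part is the sum of the second and third rows, so it is not an all-cause total.

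**Step 2: AEs by relationship.** The SAE part can fill all three relatedness levels. For non-serious events the *Not Related* row can contain only special-interest events that are not SAEs, so it is empty or nearly so. The *Definitely Related* level in Protocol section 8 calls for improvement on stopping and recurrence on re-exposure. With a single depot dose that is hard to satisfy if read literally, so most non-serious entries would probably be *Possibly Related*.

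**Step 3: which events are at risk.** The adverse-reaction list in Protocol section 6 includes transaminase rise (47%), fatigue and fever, all of which COVID-19 could also cause. Two relatedness levels can apply to the same event. *Possibly Related* admits one that has plausible timing and a known response pattern, even if other factors could readily explain it. *Not Related* covers an event for which another cause is most plausible. The site's choice between them decides whether the event is recorded.

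**Step 4: what the filter does to a comparison.** Let p_D and p_P be the true proportions with a given non-serious event in the degarelix and placebo arms, and let f be the share judged related. Assume that f is equal in the two arms, which blinding makes reasonable. The recorded proportions are then f × p_D and f × p_P, and the recorded difference is f × (p_D − p_P). The risk ratio is unchanged, but the absolute difference and the number of events shrink by the factor f. The documents give neither f nor background rates in this population, so no loss can be calculated.

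**Step 5: is there another route into the analysis?** For liver tests, none is specified. A footnote to Protocol Table 1 says that some safety laboratory results may not be entered in CRFs. The laboratory variables in SAP 3.5.2 and 3.7.3 do not include AST or ALT, and SAP 3.8 contains no laboratory safety analysis.

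**The case against.** The strongest reply is that this is a drafting conflict and not a settled decision to discard events. No sentence says that unrelated non-serious events are excluded. The collection sentence has no filter, the AE definition needs no causality, AEs appear in the schedule of events through Day 60, and the relatedness scale has a *Not Related* level. The visit-level sentence does not by itself exclude other events, and SAP 2.4.4 names an outcome without governing data entry. This stands in part: the documents contradict themselves. But the form sentence is the most specific statement of what is written down, and the DMC and outcome wording agree with it.

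A reader might infer that the planned tables are impossible to produce. The documents do not support that. The SAE halves are complete, related non-serious events can be tabulated, and the total could be read as the total of the study-related outcome in SAP 2.4.4. What is missing is an all-cause non-serious total and a usable *Not Related* row.

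A reader might also infer that events resembling COVID-19 are certain to be removed. That too goes beyond the text. *Possibly Related* can keep them, the protocol says that a definite relationship need not be shown, and *Not Related* is meant for events that are clearly unrelated. Prolonged hospitalisation and important medical events also count as SAEs, so many serious consequences are recorded regardless of cause.

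**Conclusion.** The point holds as an inconsistency with a consequence for analysis. If sites follow the form rule, the non-serious comparison in SAP 3.8.1 is filtered by attribution and its labels do not say so. SAEs and grade 3-5 arrhythmia or thromboembolic events are unaffected. Under-recording of listed degarelix reactions that overlap with COVID-19 is possible and depends on how sites apply two overlapping definitions. Its extent cannot be derived from the documents.

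The conclusion assumes that the form sentence governs data entry. If sites in fact enter all non-serious AEs under the collection sentence, the tables would be sound, but the form rule, the outcome definition and the DMC wording would then be wrong. The text needs correction either way.

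**What to change.** Reconcile Protocol section 8 (Overview, Adverse Events, Severity, and reporting to the DMC), Protocol section 10 (AE and SAE analyses), and SAP 2.4.4, 2.5.3, 3.8 and 3.8.1.

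**Preferred.** Make relatedness a field on the AE form and not a condition for completing it. In both arms, record every non-serious AE of CTCAE grade 3 or higher whatever the attribution. Apply one AE window in both documents; the protocol's 60 days and the SAP's 30 days after the last dose must be reconciled. Run the SAP 3.8.1 arm comparison on all recorded events, with related events as a secondary table, and state the recording threshold in the table titles.

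**If related-only capture is kept.** Retitle the tables as non-serious AEs judged related, plus all SAEs. Drop the total-AE comparison and the *Not Related* row for non-serious events, and make no statement about overall non-serious AE rates.

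**Cost.** The preferred route means more AE forms in an ill population. It needs no new visits or tests, because AEs are already found by record review, an AE form exists, and relationship is already a recorded item. The grade 3 threshold limits the load: any-grade capture of fever, fatigue or nausea in these inpatients would be a heavy burden. The price of the threshold is that unrelated grade 1-2 events stay uncounted. The fallback changes wording only.

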9. SAFETY MONITORING

Data and Safety Monitoring Plan

The VA Clinical Sciences Research and Development (CSR&D) centralized Data Monitoring Committee (DMC) will monitor this study. The CSR&D DMC provides an ongoing independent evaluation of the progress of studies, including patient accrual and retention, adverse events monitoring, and analysis plan. This is a service that is provided by CSR&D to ensure independent oversight of the safety and integrity of this project. No other DMC or Data and Safety Monitoring Board (DSMB) review is needed.

The DMC office is located within the Cooperative Studies Program Coordinating Center (CSPCC) at the Edward Hines, Jr. VA Hospital in Hines, IL. The DMC Office at Hines then communicates directly with the PI to provide DMC related information.

After the DMC has recommended approval for this trial to begin and the first patient has been randomized, a progress report will be due in approximately one month and then monthly thereafter. The PI typically will not need to call in for the DMC review after the

initial review. The DMC makes recommendations to the director of CSR&D for endorsement. The recommendations range from approval (unconditionally or with conditions to be addressed) to probation to termination.

Following each DMC meeting, the PI will receive meeting minutes containing any action items for which a response will be requested typically within 30 days. Then the process starts all over again for the next reporting period. In addition to the quarterly progress reports, all Serious Adverse Events are to be reported to the DMC.

Additional Safety Monitoring for AEs of Special Interest

Whereas the DMC serves as the entity with primary oversight responsibility for the study, additional real-time monitoring will be conducted to capture AEs of special interest, including cardiac arrhythmias and thromboembolic events that may result from degarelix. In particular, cardiac arrhythmias and thromboembolic complications of grades 3-5 according to CTCAE v5.0 (see Appendix C) will be closely monitored through not only ongoing, daily review of AE and SAE reports, but also through regular, planned teleconference calls to include:

- The study chair ([name]), co-chair ([name]), and the lead site coordinator ([name]),
- One or more investigators from each site and/or one or more site coordinators.

The teleconferences will occur on Tuesday of each week until the LPI + 30 days. In addition, study sites should report the onset arrhythmias of thromboembolic events of grade 3-5 according to CTCAE v5.0 within 72 hours by contacting the study chair or co-chair by email and voice call (see page 5 for contact information).

10. STATISTICAL CONSIDERATIONS

This is a randomized, placebo-controlled, double-blind phase 2 study that will compare the effects of degarelix + BCS to placebo + BCS on the clinical outcomes of patients hospitalized due to COVID-19.

Expected Treatment Effects

In a recent antiviral drug trial to treat adults hospitalized with severe COVID-19 published in the New England Journal of Medicine (NEJM) on March 18, 2020 (Cao *et al.* 2020), the results showed that a mortality rate of 17%, hospital stay rate of 50%, and ECMO or mechanical intubation rate of 11% among the patients managed with BSC after two-week follow-up. In the current study, we propose a composite endpoint of mortality, ongoing need for hospitalization, and ECMO or mechanical intubation at 15 days after randomization. We are expecting to reduce the composite endpoint rate to 35% after the degarelix treatment plus BSC from 60% for patients treated placebo plus BSC.

Sample Size Calculation and Power Analysis

The sample size estimation and power analysis shown in Table 2 are based on the hypothesis testing of the primary endpoint, which is the composite endpoint of mortality, hospital stay rate, and ECMO or mechanical intubation at 15 days after randomization (Day 15).

According to the composite endpoint outlined in the previous section, we assume that an effect size for the primary endpoint of 42% can be anticipated in the degarelix group. The other assumptions include a three-month accrual time and one-month follow-up time, and 2:1 sample allocation of degarelix: placebo treatment group. The sample size for the study is estimated based on a superiority trial design. To have 90% power of detecting the expected 42% reduction using a two-sided two proportion test with a significance level of 0.05 in the degarelix compared to the placebo group will require 186 evaluable patients total (i.e. 124 evaluable patients in the degarelix group and 62 evaluable patients in the placebo group). Based on an assumed 5% attrition rate, 198 patients will be required (i.e. 132 in the degarelix group and 66 in the placebo group) to achieve actual statistical significance at alpha level of 0.05 and power of 90% (see Table 2).

Table 2: Sample Size Estimation and Power Analysis

Effect Size	Treatment Arms	Testing Power		
		80 %	85 %	90 %
30 %	Degarelix + BSC	186	210	244
	Placebo + BSC	93	105	122
	Total	279	315	366
42%	Degarelix + BSC	96	108	124
	Placebo + BSC	48	54	62
	Total	144	162	186
50%	Degarelix + BSC	64	72	84
	Placebo + BSC	32	36	42
	Total	96	108	126

Duration of Study and Number of Participating Sites

To estimate the expected study duration and resources, we assume that the recruitment rate will be half of what we anticipate. Under this assumption, various scenarios were examined in order to identify an optimal combination between the number of sites, the study duration (which includes recruitment period and follow-up period) and the estimated budget. The study will include four VA medical centers and each center will randomize 17 patients per month on average; however, estimated recruitment rate will vary depending on the patient volume of each participating center as the disease evolves. Based on these assumptions, the recruitment period was found to be approximately three

months. This will be followed by approximately one month of follow up for the last patients randomized into the study followed by one month of data analysis. Thus, the study duration including start-up will be approximately five months.

Interim Analysis and Criteria for Study Termination

A mid-term interim analysis of the primary endpoint will be performed at half of the patients or 99 randomized patients complete or are terminated the study. If the mid-term analysis of the primary endpoint indicates that the null hypothesis can be rejected with a boundary value of 2.77 (standardized $Z > 2.77$ or < -2.77) at an α -level of 0.006 or accepted with a boundary value of 0.44 ($-0.44 \leq \text{standardized } Z \leq 0.44$) based on O'Brien and Fleming criteria, the study will be recommended for trial termination for efficacy and futility reasons (shown in the Figure 1). Enrollment will be paused if the interim analysis results indicate crossing of the threshold for futility or efficacy until the final DMC recommendation is rendered.

Meanwhile, the drug toxicity will be closely monitored and analyzed. As described in previous sections, arrhythmia and thromboembolic complications are adverse events of special interest that will be monitored closely and graded according to on CTCAE 5.0. Once the toxicity markers reach a threshold of 25% (Ray and Rai 2011), a statistical analysis of the toxicity will be performed. If the experimental (degarelix) group has a significant higher toxicity compared to the placebo group at an α -level of 0.01, then results will be reported to the DMC for a recommendation for trial termination.

[figure not shown]

Figure 1. Interim analysis stopping boundaries for efficacy and futility

Data Analysis Plan

The primary analysis will be performed to test the null hypothesis of no difference in composite outcome of mortality, hospital stay rate, and ECMO or mechanical intubation at 15 days after randomization between the degarelix + BSC versus placebo + BSC, i.e. odds ratio equals one. If the null hypothesis is not rejected, a 95% confidence interval will be constructed about the difference observed to inform the medical community as to how large the difference is likely to be in either direction. All statistical tests will be two-sided, and the primary outcome will be tested at 5% level of significance. SAS 9.4 or higher will be used to conduct all the statistical analyses. A variety of analytic methods will be used for the primary endpoint, secondary endpoints, exploratory endpoints analyses, and other analyses (Table 3).

Analysis Populations

Intent-to-Treat (ITT) – This population is defined as the population of patients who will be randomized to either of the treatment groups – degarelix or placebo. The patients will be categorized (in terms of their treatment assignment) based on their initial randomized group and will be included in analyses irrespective of their status – completer or drop out of the study before completion. The testing power for the primary endpoint is estimated as 90% in this population.

Safety – This population includes all patients who will be randomized to either of the treatment groups – degarelix or placebo.

The primary analysis of the study will be performed on the primary endpoint on the ITT population. SAEs will be analyzed based on the Safety population.

Primary Endpoint Analysis

The primary study endpoint will be the composite outcome of mortality, ongoing need for hospitalization, and ECMO or mechanical intubation at 15 days after randomization. This outcome will be compared according to assigned treatment groups, using Pearson χ^2 test. The test for differences between the treatment groups in the primary outcome will be conducted at an overall α -level of 0.05 (i.e. $\alpha = 0.006$ for mid-term interim analysis, $\alpha = 0.044$ for the final analysis). If a patient drops out from the study, then he will be considered as a failure. Additional analyses will be conducted using logistic models to adjust for other clinical factors, such as age, hypertension, and COPD. Logistic regression will be used for the primary endpoint ($y = 1$ if a composite outcome, otherwise $y = 0$) analysis with the treatment group as the testing factor (x). The following covariates will be included in the model: age (z_1), hypertension (z_2), and COPD (z_3), site (z_4). Given the composite outcome probability $p = p(y = 1|x, z_1, z_2, z_3)$, the basic model is defined as follows:

$$\text{Logit}(p) = \ln\left(\frac{p}{1-p}\right) = \beta_0 + \beta_1 x + \beta_2 z_1 + \beta_3 z_2 + \beta_4 z_3$$

Odds ratio and 95% confidence interval (CI) will be presented using SAS PROC GENMOD or PROC LOGSTIC. If the coefficient for treatment effect is significant, then

the null hypothesis will be rejected. Logistic models will be tested for goodness of fit. We will assess goodness-of-fit using the statistic -2 log likelihood, which has a χ^2 distribution under the null hypothesis that all the explanatory variables in the model are zero. We will also consider the Akaike Information Criterion statistic and the Schwartz Criterion statistic, both of which adjust the -2-log likelihood for the number of items in the model. Models that show lack of fit will be reconsidered for the inclusion of additional variables or use of alternate models with assumptions that are better met by the study data. One alternate model if model fit is poor for logistic regression is a log-linear model.

Further, Cochran Mantel-Haenszel method will be used to adjust for three randomization stratification factors (Age: <65 vs. \geq 65, History of hypertension: yes vs. no, and Influenza severity scale: 3 vs 4/5) using SAS PROC FREQ as one of the sensitivity analyses for the primary efficacy endpoint.

Secondary Endpoint Analyses

Secondary endpoints included in the data analysis are the composit endpoint at 30 days after randomization, time to clinical improvement, inpatient mortality, length of hospital stay, length of intubation for mechanical ventilation, time to normal temperature, and the maximum severity of COVID-19 illness, which are defined in the endpoint section. The secondary endpoint analyses will be adjusted for multiplicity with a α -level of 0.0071 for each endpoint.

The composite outcome of mortality, ongoing need for hospitalization, and ECMO or mechanical intubation at 30 days after randomization as a secondary endpoint will be analyzed using the methods described in the the primary endpoint analysis.

For the time to clinical improvement as defined by a decline of 2 categories or more from the baseline on the modified 7-category ordinal scale of clinical status of hospitalized influenza patients (influenza scale, see Appendix A) or hospital discharge (see section 2 for definition of discharge) whichever comes first, survival analysis techniques will be used to analyze the time-to-event data for this endpoint. Patients whose conditions getting worse or died or withdraw from the study without clinical improvement will be censored. Kaplan-Meier analysis will be used to compare the two curves of the time to the clinical improvement over the patient follow-up time between the two treatment groups and a log-rank statistic will be used to test the equality of the survival function estimates of the two treatment groups using SAS PROC LIFETEST. Kaplan-Meier curves will be created. Additional analysis will be conducted using the Cox's Proportional Hazards model to test the treatment efficacy of the treatment intervention on the time until endpoint events adjusted for three prognostic factors: age, hypertension, and COPD. The hazard ratio and 95% confidence interval (CI) will be presented using SAS PROC PHREG. If the coefficient for treatment effect is significant, then the null hypothesis will be rejected. The regression model will be checked for the model assumption, adequacy, and the goodness of fit. If the model shows lack of fit, then alternate models with assumptions that are better met by the study data will be considered.

For mortality endpoint data analysis, the treatment effect will be analyzed initially with a Pearson χ^2 test and logistic regression will also be performed using SAS PROC

LOGISTIC by taking account of prognostic factors described in the primary endpoint analysis.

For the length of hospital stay data analysis, medians (interquartile ranges) will be presented and Wilcoxon tests, a nonparametric method, will be performed to compare the medians of the length of hospital stay between the two treatment groups using SAS PROC NPAR1WAY. In addition, a quantile regression will be used to test the effect of the treatment on the time until the clinical event adjusted for prognostic factors described in the primary endpoint analysis.

For the length of intubation for mechanical ventilation data analysis, nonparametric analyses will be performed as described in the length of hospital stay analysis.

For time to normal temperature data analysis, survival analysis techniques will be used as described in the time to the clinical endpoint analysis using SAS PROC LIFETEST and PROC PHREG.

For the maximum severity of COVID-19 illness data analysis, Pearson χ^2 test will be performed for this categorical endpoint using SAS PROC FREQ initially. Given the endpoint is also an ordinal variable, Cochran–Armitage test will be performed to test the ordinal trend tendency using SAS PROC FREQ. in addition to the frequency analysis, proportional odds logistic regression will also be performed using SAS PROC LOGISTIC by taking account of the factors of age, hypertension, COPD, and the baseline influenza scale (see Appendix A).

Exploratory Endpoint Analyses

Clinical and Laboratory Prognostic Factors

Exploratory analyses will be performed to identify the impact of clinical and laboratory prognostic factors on the primary endpoint or any secondary endpoint. Clinical factors include age, presence or absence of COPD, hypertension, or cardiovascular disease, or use of angiotensin converting enzyme inhibitors. Laboratory measurements including D-dimer, IL-6, LDH, ferritin, total WBC, absolute neutrophil count (ANC), absolute lymphocyte count (ALC), and testosterone are measured during the patient's hospital stay. Further germline genomic factors will also be analyzed if feasible as prognostic factors for the study outcomes for part of the patients.

For continuous variables, the sample size, mean, SD, median, minimum, and maximum values for each intervention will be presented for each parameter at each data collection time point and tested using SAS PROC TTEST between the treatment groups. If a variable is not normally distributed the non-parametric method will be applied using SAS PROC NPAR1WAY. For categorical variables, the number and percentage of patients by the treatment group will be tabulated and tested based on Pearson χ^2 test using SAS PROC FREQ.

Univariate correlation with the primary endpoint or any categorical secondary endpoint will be assessed for each clinical and laboratory factor based on logistic regressions using SAS PROC LOGISTIC. For the secondary endpoints of time to events data, univariate analysis will be performed based on Cox regressions using SAS PROC PHREG. For the secondary endpoints of length of hospital stay and length of intubation for mechanical ventilation, nonparametric univariate analysis will be performed based on Spearman correlation method using SAS PROC CORR for the continuous prognostic factors, whereas Mann–Whitney U or Wilcoxon rank-sum test will be performed for the categorical prognostic factors using SAS PROC NPAR1WAY. For those prognostic factors significantly associated with the primary and secondary outcomes from the univariate analyses, multiple regressions will be performed by adjusting some other prognostic factors identified from the univariate analyses. The multiple regressions will be performed as described in the primary analysis and each corresponding secondary endpoint analysis.

Viral Load, Cytokines Levels, and TMPRSS2 Expression

To explore the mechanisms that underlie treatment effect, nasopharyngeal (NP) epithelial or peripheral blood mononuclear cell (PBMC) TMPRSS2 expression, NP and plasma viral load, or serum cytokine (TNF- α , IL-1 β , IL-6) levels will be tested among the patients from the Great Los Angeles site, only.

Viral load kinetics in the two treatment groups over patients' critical period will be monitored from baseline to Day 15. The viral load in plasma will be assessed by the viral RNA measured by a reverse-transcriptase–polymerase chain–reaction (RT-PCR) assay and quantified as \log_{10} copies/ml. Mean change from baseline in SARS-CoV-2 viral RNA load across each sample collection time point will be compared by the treatment groups. The mean value for \log_{10} copies/ml for each week will be calculated and summarized. \log_{10} copies/ml changes from baseline to each week will be summarized. For each week, the sample size, mean, SD, median, minimum, and maximum values for each treatment will be presented. A mixed-effect model of repeated measure (MMRM) for overall changes across all the time point between the two treatment groups using SAS PROC MIXED. A longitudinal graph of \log_{10} copies/ml will be created and presented by 95% confidence intervals of the means.

Serum cytokines TNF- α , IL-1 β , and IL-6, as well as TMPRSS2 expression and anti-viral antibodies will be tested by immunoassays. Mean change from baseline in the cytokine and TMPRSS2 levels, and antibody titers across each sample collection time point will be compared by the treatment groups. The mean value for each week will be calculated and summarized. Mean changes from baseline to each week will be summarized. For each week, the sample size, mean, SD, median, minimum, and maximum values for each treatment will be presented. A mixed-effect model of repeated measure (MMRM) for overall changes across all the time point between the two treatment groups using SAS PROC MIXED. A longitudinal graph of each measurement level will be created and presented by 95% confidence intervals of the means. If a measurement level

is not normally distributed, then a non-parametric method will be used as an alternative analysis approach.

The exploratory analyses will not be adjusted for multiplicity.

AE and SAE analyses

